### **Informed Consent**

The IRB/IEC approved informed consent will be signed by the subject before beginning any study-specific procedures. Details about how informed consent will be obtained and documented are provided in [Section 9.3](#).

### **Gynecological (Pelvic and Breast) Examination**

A complete breast, and pelvic examination, including external genitalia will be performed during the Month 6 or Premature Discontinuation Visit in the Treatment Period.

### **Pap Test**

A Pap test will be performed at Treatment Period Month 6 or Premature Discontinuation Visit.

A Pap test will be collected using the Thin Prep® Pap Test™ provided and analyzed by the central laboratory. If the subject is experiencing menstrual bleeding that precludes the

performance of the Pap test, this procedure should be performed as soon as possible after the menstrual bleeding has ended. In the case of an unsatisfactory sample, the Pap test should be repeated. The repeat Pap test should be performed when the subject is not experiencing menstrual bleeding.

Subjects who have Pap test results that require additional evaluation should follow local guidelines or standard of care. In addition, the AbbVie TA MD should be notified to discuss subject's management plan for any clinically significant pathologic findings during the Post-Treatment Follow-Up Period.

All subjects will continue in the Post-Treatment Follow-Up Period. Subjects who may require colposcopy will enter the Post-Treatment Follow-Up Period and should be treated per local guidelines or standard of care.

### **Endometrial Biopsy**

Instructions on endometrial biopsy collection and processing procedures for shipping will be provided by the central laboratory. Sites can use the endometrial biopsy instruments provided by the Central Lab or any other endometrial biopsy instruments available at the study site. Subjects must have a confirmed negative urine pregnancy test within 24 hours prior to undergoing the endometrial biopsy.

Pre-medication for the endometrial biopsy procedure is allowable and should be recorded in source documents and on the appropriate eCRF. Misoprostol for cervical dilatation is allowable. An office hysteroscopy may be performed to obtain the endometrial biopsy sample if the endometrial biopsy cannot be performed because of anatomical reasons.

An endometrial biopsy will be performed at the Treatment Period Month 6 Visit or at the Premature Discontinuation Visit (if the subject prematurely discontinues after the Month 3 Visit).

If the endometrial biopsy is performed on the same day as the Pap smear or pelvic ultrasound, the endometrial biopsy should be performed after the Pap smear and pelvic ultrasound.

In the event that the Month 6 or Premature Discontinuation Visit endometrial biopsy cannot be performed (e.g., due to a stenotic cervix or location of fibroids), or an insufficient biopsy sample is obtained and the concurrent TVU indicates a thickness of > 4 mm, a repeat biopsy must be performed. If upon repeat, a sample cannot be obtained or remains insufficient, the AbbVie TA MD should be consulted.

Subjects with abnormal endometrial pathology results at Treatment Month 6 will enter the Post-Treatment Follow-Up Period and should be managed according to standard of care. The subject's management plan for any of these significant pathologic findings should be reviewed with the AbbVie TA MD, and the subject outcome documented in the eCRF.

### **Physical Examination**

During the Treatment Period and Post-Treatment Follow-Up Periods, a complete physical examination will be performed at Treatment Period Month 6 and Post-Treatment Follow-Up Month 6 or Premature Discontinuation Visits. The complete physical examination will include weight measurements. Symptom-directed physical examinations will be performed as specified in [Appendix C](#), Study Activities.

Any clinically significant physical examination findings will be recorded in the source documents and in the eCRFs as adverse events.

### **Vital Signs**

Vital sign determination of heart rate, blood pressure, respiratory rate and body temperature will be obtained at all visits during the study as indicated in [Appendix C](#), Study Activities. The blood pressure and heart rate measurements should be taken prior to scheduled blood collections. Body temperature measurements should be assessed using

the same modality consistently throughout the study, e.g., oral, aural, axillary, etc., and the modality will be reported in the source documents and eCRF.

### **12-Lead Electrocardiogram (ECG)**

During the Treatment Period, a resting 12-lead ECG will be conducted at the Month 6 Visit or Premature Discontinuation Visit (if applicable) as indicated in [Appendix C](#), Study Activities.

The Investigator or qualified designee at the study site will determine if any findings outside the normal physiological variation are clinically significant (in consultation with a cardiologist if necessary), and document this on the ECG tracing/report with signature and date. The original ECG tracing or a certified copy of the original tracing with the physician's assessment will be retained in the subject's records at the study site. For ECG with QT interval corrected for heart rate (QTc) > 450 msec, the correction formula used (i.e., Bazett's or Fridericia's) and the corrected result should be recorded in source documents and eCRF. The study site should use the same correction formula used in the respective pivotal study and continue to consistently use throughout this study.

### **Mammogram**

All subjects who had a mammogram performed to determine eligibility into their respective Pivotal Study, will have a mammogram performed at Treatment Period Month 6 or at the Premature Discontinuation Visit if it has been approximately 12 months since the screening mammogram was performed.

### **Central Imaging Procedures**

Fibroid and uterine assessments will be obtained using pelvic ultrasound (TAU and TVU) throughout the study. In addition to the TAU and TVU, an MRI will continue to be performed in the subset of subjects who consented and participated in the MRI Subset during their respective pivotal study. The MRI subset will continue to evaluate uterine fibroid size and volume and uterine volume using another technique in addition to ultrasound.

All ultrasound and MRI images will be sent to the Central Imaging Core Lab (ICL) for review to monitor safety during the Treatment and Post-Treatment Follow-Up Periods.

The pelvic ultrasound (TAU, TVU) and/or SIS and MRI (if applicable) will be performed by the Investigative Sites' or affiliated Radiology Department. The Ultrasonographer at each Investigative Site will be required to acquire the ultrasound and MRI (if applicable) images according to the Imaging Acquisition Guidelines provided by the ICL. Images should be sent/transmitted to the ICL for subject evaluation during the course of the study. Refer to the Image Acquisition Guidelines for instructions on submitting images to the ICL.

The pelvic ultrasound (TAU, TVU), and/or SIS and MRI (if applicable) will be assessed both locally and by the ICL. If images are unevaluable, the ICL will inform the Investigative Site and additional images will need to be resubmitted. If there is a discrepancy between the local assessment and the central reader's assessment, this should be brought to AbbVie's attention and AbbVie will discuss the findings with the local site and central reader on a case-by-case basis. The Investigator or designee should consult the local ultrasound and SIS reports and/or images in order to make any safety-related judgments concerning the subject. The interpretation of the local report and/or images will be filed or recorded in the subject's source documents. Data and/or local interpretation from the local ultrasound and SIS images will not be recorded in the eCRF unless associated with a significant finding or adverse event.

During the Treatment and Post-Treatment Periods, the ICL may issue a report if any significant changes are observed that may affect subject safety during the study. In these cases, the Investigator should review the local ultrasound and/or MRI images and treat as per standard of care.

The pelvic ultrasound, and MRI (if applicable) will be performed as specified in [Appendix C, Study Activities](#).

### **Pelvic Ultrasound: TAU and TVU**

Pelvic ultrasounds (TAU and TVU) will be performed at Treatment Period Month 3 and Month 6 and at Post-Treatment Follow-Up Period at Month 3 and Month 6 or at the time of premature discontinuation (if not performed within the past 2 months). Assessments for the pelvic ultrasound include, but are not limited to the following:

- Endometrial thickness
- Presence of abnormal endometrial appearance or endometrial pathology
- Presence of uterine fibroids
  - Number of uterine fibroids
  - Volume and location of the 3 largest fibroids
- Uterine volume in cubic centimeters
- Presence of ovarian cysts
  - Number
  - Size (cm)
  - Location (right or left ovary)
  - Simple versus complex
- Endometrioma > 3.5 cm longest diameter
- Solid ovarian lesions > 1.5 cm longest diameter

### **Magnetic Resonance Imaging (MRI) Subset:**

Subjects who participated in the MRI subset in the Pivotal Studies will continue to be included in the MRI subset in this study.

An MRI will be performed at the Month 6 or Premature Discontinuation Visit during the Treatment Period and at the Post-Treatment Follow-Up Month 3 Visit. Subjects who had an MRI performed in the past 3 months prior to prematurely discontinuing are not required to repeat the MRI at the time of Premature Discontinuation during the Treatment or Post-Treatment Follow-Up Period.

Assessments for the MRI include, but are not limited to the following:

- Fibroid volume in cubic centimeters (of 3 largest fibroids)
- Fibroid location
- Uterine volume in cubic centimeters
- Presence of adenomyosis (diffuse adenomyosis as the dominant condition versus focal)
- Presence of any concerning findings

Depending on the size of the uterus, MRI images of the abdominal cavity may need to be submitted to measure uterine volume and to assess for safety. It is recommended to follow standard of care when determining which anatomical sections are to be included in order to prevent incomplete views, thus leading to repeat procedures. Please refer to the Image Acquisition Guidelines for further details.

#### **Intracavitary Uterine Findings**

An SIS may be performed during the Treatment or Post-Treatment Follow-Up Periods when the pelvic ultrasound (TAU and TVU) or MRI (if applicable) results suggest an intracavitary lesion such as a polyp. The finding of a polyp during the Treatment or Post-Treatment Follow-Up Periods should be documented as an adverse event if the Investigator considers it to be clinically significant.

The AbbVie TA MD should be notified of the subject's management plan for any clinically significant pathologic findings during the Treatment and Post-Treatment Follow-Up Periods.

#### **Ovarian Findings:**

During Treatment or Post-Treatment Follow-Up Periods, if the pelvic ultrasound shows a simple ovarian cyst > 5 cm or a complex ovarian cyst (including endometriomas) > 3.5 cm in longest diameter the findings should be documented as an adverse event if the Investigator considers them to be clinically significant.

### **Bone Mineral Density (DXA Scan)**

[figure not shown]
DXA scans of the spine, femoral neck and total hip will continue to be performed by qualified technologist/radiologists utilizing GE Lunar or Hologic equipment and sent to an ICL for review and analysis. The same instructions on calibration and standardization of instruments as used in the pivotal studies and as specified in the manual provided to all study sites should be used.

### **DXA Scans Performed in the Treatment Period**

DXA scans are required to be performed during the Treatment Period as follows:

- Month 3: Only for those subjects with BMD decrease  $\geq 5\%$  in the spine **or** total hip at Month 6 of their respective pivotal study (Studies M12-815 or M12-817) as determined by the central reader
- Month 6: All subjects

**Figure 2. Management of BMD % Decrease: Treatment Period and Post-Treatment Period**

Management of BMD % Decrease on DXA scan obtained at **Treatment Month 3**:

- Subjects with BMD decrease  $\geq 8\%$  in the spine, femoral neck **or** total hip will discontinue study drug treatment and enter the Post-Treatment Follow-Up Period to have the required BMD evaluation at Follow-Up Months 6 and 12.
- Subjects with BMD decrease  $\geq 5\%$  and  $< 8\%$  in the spine **or** total hip will continue in treatment and will require a DXA scan at Treatment Month 6.

### **DXA Scans Performed in the Follow-Up Period**

DXA scans will be performed in the Follow-Up Period as follows:

- Follow-Up Month 6
- Follow-Up Month 12
- Follow-Up Premature Discontinuation visit **unless** the subject prematurely discontinued from Follow-Up and had a study DXA scan within approximately 1 month prior to the Follow-Up Premature Discontinuation Visit.

#### **Management of BMD % Decrease from Baseline for Subjects Who Prematurely Discontinue in the Follow-Up Period**

Subjects who prematurely discontinue at the time of or after the Month 3 study visit will and have a Follow-Up Premature Discontinuation DXA scan performed will be referred to a bone specialist for further evaluation utilizing the criteria listed below for referral at the end of the 12 Month Follow-Up Period.

#### **Management of BMD % Decrease at Post-Treatment Follow-Up Month 12**

Management of subjects with BMD % decrease at Post-Treatment Follow-Up Month 12 is outlined below and illustrated in [Figure 3](#).

Subjects with Post-Treatment Month 12 BMD % decrease of < 3% in the spine, femoral neck and total hip and no decrease in any region from Post-Treatment Follow-Up Month 6 to Month 12 will not require a referral to a bone specialist.

Subjects will be referred to a Bone Specialist at Post-Treatment Follow-Up Month 12, even if the overall BMD decrease from baseline is < 3%, if they meet the following criteria:

[figure not shown]
- Subject had Post-Treatment Month 6 BMD decrease compared to baseline (of the Pivotal Study) in any region and demonstrates further BMD decrease at Month 12 in the same region (between Post-Treatment Month 6 and Month 12) and, subject meets one of the following:
    - Subject was  $\geq 45$  years of age at the time of last dose of study drug in the Treatment Period
- OR

- Subject has not had a menses in the past 12 months
- Subjects with Post-Treatment Month 12 BMD % decrease of  $\geq 3\%$  in the spine, femoral neck or total hip and a T-score  $< -1.0$  OR T-score  $< -1.5$  will be referred to a bone specialist for further management, and will be followed on an individual basis.

The management plan for subjects referred to a Bone Specialist (e.g., Endocrinologist, Rheumatologist, International Society for Clinical Densitometry (ISCD) certified physician) will be reviewed with the AbbVie TA MD; this includes, follow-up information on the subject evaluation, treatment, and outcome. Follow-up information from the initial evaluation will be recorded in the eCRF. It is recommended that the bone specialist should be someone other than the Principal Investigator or Sub-Investigator.

Subjects who do not meet any of the above criteria will not require additional BMD follow-up.

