**Figure 3. Management of BMD % Decrease: Post-Treatment Follow-Up Month 12**

Note: If criteria is not met, no referral to bone specialist is required.

The baseline DXA is the Screening DXA performed in the respective Pivotal Study M12-815 or Study M12-817. In the event that there is a change in DXA machine for a subject between baseline and a subsequent time-point, the AbbVie TA MD must be consulted.

A BMD decrease at any anatomic location (spine, total hip or femoral neck) during the Treatment or Post-Treatment Follow-Up Period that leads to premature discontinuation from study or a BMD decrease at any anatomic location with a T-score < -1.5 should be reported as an adverse event.

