## **6.0 Complaints**

A Complaint is any written, electronic, or oral communication that alleges deficiencies related to the physical characteristics, identity, quality, purity, potency, durability, reliability, safety, effectiveness, or performance of a product/device after it is released for distribution.

Complaints associated with any component of this investigational product must be reported to the Sponsor (Section 6.2.2). For adverse events, please refer to Section 6.1 through Section 6.1.5. For product complaints, please refer to Section 6.2.

All adverse events will be followed to a satisfactory conclusion.

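### The follow-up Month 12 no-referral sentence has no T-score exception, so it exempts some women whom the last referral bullet, on its best reading, requires to be referred

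*Protocol*

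**What the plan says.** The rules are in Protocol section 5.3.1.1, under the heading on managing BMD decrease at follow-up Month 12. In order:

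- **Exemption.** Women with less than 3% loss from baseline at total hip, femoral neck and spine, "and no decrease in any region from Post-Treatment Follow-Up Month 6 to Month 12 will not require a referral to a bone specialist".
- **Lead-in to the referral list.** Women will be referred "even if the overall BMD decrease from baseline is < 3%, if they meet the following criteria".
- **First bullet.** A region already below baseline at follow-up Month 6 has fallen further by Month 12, and the woman was at least 45 at her last dose or has had no menses for 12 months.
- **Last bullet.** Women with at least 3% loss at any of the three sites and a T-score below -1.0, OR a T-score below -1.5, "will be referred to a bone specialist for further management, and will be followed on an individual basis". No bracket or comma groups the three conditions.
- **Closing sentence.** "Subjects who do not meet any of the above criteria will not require additional BMD follow-up".
- **Note under Figure 3.** "If criteria is not met, no referral to bone specialist is required". The figure itself is not shown.

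Three related rules bear on the reading. After Figure 3, and again in section 6.1.1.1, the protocol says that "a BMD decrease at any anatomic location with a T-score < -1.5 should be reported as an adverse event". Women who leave follow-up early are judged "utilizing the criteria listed below for referral at the end of the 12 Month Follow-Up Period". SAP section 12.4.2 plans two separate follow-up listings: at least 3% decrease with T-score below -1.0 in the same region, and T-score at or below -1.5 alone.

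**The concern.** The exemption looks only at the size of the loss and the trend from Month 6 to Month 12. The last bullet also uses the absolute T-score. If a T-score below -1.5 is a trigger in its own right, the two sentences give opposite instructions for a woman with a small, stable loss and a low T-score. One says that she needs no referral; the other says that she will be referred.

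This is an operative safety threshold, and two sites could apply it differently to the same woman. Referral also sets further steps in motion: the specialist's plan is reviewed with the sponsor's medical director, and findings from the first evaluation go into the eCRF. A woman treated as exempt would not get these through the referral route.

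**Working it through.** There is no stated figure to reproduce. The check is one of logic, with one illustrative calculation on an outside assumption.

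**1. How does the last bullet group?** There are two natural readings.

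- Reading A: (loss >= 3% and T < -1.0) OR T < -1.5.
- Reading B: loss >= 3% and (T < -1.0 OR T < -1.5).

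Any T-score below -1.5 is also below -1.0, so the bracket in B reduces to T < -1.0 and the -1.5 cut-off decides nothing. Three things point to A: the lead-in allows referral below 3% loss; the two SAP listings are reading A split in two; and the adverse-event rule uses -1.5 with no 3% threshold. (The SAP listing uses <= -1.5 where the protocol uses < -1.5, a small separate mismatch.)

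**2. Can a referral rule fire for an exempt woman?** Exempt means loss < 3% at all three sites and no fall from Month 6 to Month 12.

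| Referral trigger | Requires | Possible if exempt? |
|---|---|---|
| First bullet | a further fall from Month 6 to 12 | No |
| Last bullet, first limb | loss >= 3% | No |
| Last bullet, second limb (A) | T < -1.5 | Yes |

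The overlap is therefore exactly one group: small loss, no further fall, T-score below -1.5. As a cross-check, take 2 loss classes x 3 trend classes (no further fall; further fall without the first bullet met; further fall with it met) x 3 T-score bands = 18 cells. Under A, 1 cell is both exempt and referred; under B, none. These are cells of a table, not women.

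**3. Example.** Loss 1%, no further fall, T-score -1.8. Exemption: 1% < 3% and no fall, so no referral. Last bullet under A: -1.8 < -1.5, so referral.

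**4. Could such a woman exist?** The documents give neither a T-score distribution nor the pivotal studies' baseline T-score limit. Assume that the young-adult coefficient of variation of BMD, cv, is 10% to 13% (not in the documents). After a 2.9% loss, T = -1.5 corresponds to a baseline BMD, relative to the young-adult mean, of (1 - 1.5 x cv)/(1 - 0.029), and baseline T is that value minus 1, divided by cv.

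- cv = 0.10: 0.85/0.971 = 0.8754, so T = -1.25.
- cv = 0.13: 0.805/0.971 = 0.8290, so T = -1.32.

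On that assumption, a woman entering with a T-score below about -1.25 to -1.32 could reach the conflicting group with a loss just under 3%.

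**The case against.** The strongest reply is that the text resolves itself: a general statement comes first, a specific override follows, and the Figure 3 note withholds referral only when no criterion is met. Much of this stands as evidence of intent. It does not fully remove the conflict. The lead-in overrides the size condition of the exemption but says nothing about a woman who also meets the no-further-fall condition. Since the first bullet always needs a further fall, a site could take the lead-in to concern that bullet alone. The closing sentence is about further BMD follow-up rather than referral.

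Second, Figure 3 is not visible, and layout that separated the conditions may have been lost in the text. That stands: the figure may show the intended grouping. The exemption sentence would still lack an exception.

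Third, harm is partly covered. The woman in the example has a BMD decrease with a T-score below -1.5, so hers is an adverse event, and "All adverse events will be followed to a satisfactory conclusion". Saying that referral is not required does not forbid it. This also stands, although adverse-event follow-up is not the same as specialist referral.

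A reader might infer two stronger points that the documents do not support. One is that the -1.5 cut-off may have no effect at all; that needs reading B, which the separate SAP listings and the stand-alone adverse-event trigger make implausible. The other is that the contradiction extends to women who leave follow-up early. That rule brings in only the referral criteria, so no clash with the exemption arises there, although the missing brackets still leave the bullet less clear than it should be.

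**Conclusion.** The concern holds as a minor defect in safety wording. The exemption and the last referral bullet contradict each other for women with less than 3% loss at all sites, no fall from follow-up Month 6 to Month 12, and a T-score below -1.5. The conclusion rests on reading A, which the documents favour, and is subject to what Figure 3 shows. The intended rule is probably that referral prevails.

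The number of women affected cannot be stated, and the cell count in the check should not be read as a rate. Nor should a reader infer that these women go unmonitored or that results are at risk: the adverse-event rule applies to them, and no efficacy or BMD analysis depends on this referral rule.

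**What to change.** Make two wording changes in Protocol section 5.3.1.1:

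1. Begin the no-referral sentence with *Unless they meet any referral criterion below,*.
2. Write the conditions of the last bullet as *(>= 3% decrease in the spine, femoral neck or total hip and T-score < -1.0) OR (any BMD decrease from baseline with T-score < -1.5)*.

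Then confirm that Figure 3 agrees. The BMD-decrease condition in the second limb matters: without it, the bullet would require referral of women with no loss, or a gain, whose T-score was already low. The section concerns BMD decrease, and the adverse-event rule also requires one. With both changes, no woman is both exempted and referred, and the -1.5 cut-off keeps its effect.

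No procedure, visit or analysis is added to the plan. The cost is a short clarification to sites and a re-check of women already past follow-up Month 12 or already discontinued from follow-up.
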